### **8.2.5.3. Management of Hyperglycemia**

Hyperglycemia is defined as the following:

- Fasting glucose  $\geq 270$  mg/dL (15.0 mmol/L) using glucometer (or central laboratory).

After randomization, participants noted to have a fasting glucose value (during home glucose monitoring) meeting the above definition of hyperglycemia must be instructed to repeat the measurement the next day (following at least an 8 (preferably 10) hour fast, except water). If the second measurement also meets the above definition, participants must be asked to return to the site a day later (following at least an 8 (preferably 10) hour fast, except water) and have blood collected for fasting plasma glucose (and shipped to the central laboratory for analysis).

The investigator should determine if the participant collected the samples after an adequate fasting period; and if the participant is following recommended dietary guidelines. Proper dietary and collected procedures should be reinforced with the participant.

If the results from the central laboratory confirm the readings using glucometer, the participant should receive glycemic rescue medication at the discretion of the investigator (see [Section 6.5.5](#)).

### **8.2.6. Clinical Laboratory Assessments**

See [Appendix 2](#) for the list of clinical safety laboratory tests to be performed and the [SoA](#) for the timing and frequency.

The investigator must review the laboratory report, document this review, and record any clinically relevant changes occurring during the study in the AE section of the CRF. Clinically significant abnormal laboratory findings are those which are not associated with the underlying disease, unless judged by the investigator to be more severe than expected for the participant's condition.

All laboratory tests with values considered clinically significantly abnormal during participation in the study or within 28 to 35 days after the last dose of study intervention should be repeated until the values return to normal or baseline or are no longer considered clinically significant by the investigator or medical monitor.

If such values do not return to normal/baseline within a period of time judged reasonable by the investigator, the etiology should be identified and the sponsor notified.

All protocol-required laboratory assessments, as defined in [Appendix 2](#), must be conducted in accordance with the laboratory manual and the [SoA](#).

If laboratory values from non-protocol-specified laboratory assessments performed at the institution's local laboratory require a change in participant management or are considered clinically significant by the investigator (eg, SAE or AE or dose modification), then the results must be recorded in the CRF.

### **8.2.7. Pregnancy Testing**

Pregnancy tests will be both urine and serum tests, and must have a sensitivity of at least 25 mIU/mL. Pregnancy tests will be performed in all females at the times listed in the [SoA](#). Following a negative pregnancy test result at screening, appropriate contraception must be commenced and a second negative pregnancy test result will be required at the baseline visit prior the participant's receiving the IP. Pregnancy tests will also be done whenever 1 menstrual cycle is missed during the active treatment period (or when potential pregnancy is otherwise suspected) and at the end of the study. Pregnancy tests may also be repeated if requested by institutional review boards (IRBs)/ethics committees (ECs) or if required by local regulations.

### **8.3. Adverse Events and Serious Adverse Events**

The definitions of an AE and an SAE can be found in [Appendix 3](#).

AEs will be reported by the participant (or, when appropriate, by a caregiver, surrogate, or the participant's legally authorized representative).

The investigator and any qualified designees are responsible for detecting, documenting, and recording events that meet the definition of an AE or SAE and remain responsible to pursue and obtain adequate information both to determine the outcome and to assess whether it meets the criteria for classification as an SAE or that caused the participant to discontinue the study intervention (see [Section 7](#)).

In addition, the investigator may be requested by Pfizer Safety to obtain specific follow-up information in an expedited fashion.

### **8.3.1. Time Period and Frequency for Collecting AE and SAE Information**

The time period for actively eliciting and collecting AEs and SAEs (“active collection period”) for each participant begins from the time the participant provides informed consent, which is obtained before the participant’s participation in the study (ie, before undergoing any study-related procedure and/or receiving IP), through and including a minimum of 28 calendar days, except as indicated below, after the last administration of the IP.

For participants who are screen failures, the active collection period ends when screen failure status is determined.

Follow-up by the investigator continues throughout and after the active collection period and until the event or its sequelae resolve or stabilize at a level acceptable to the investigator, and Pfizer concurs with that assessment.

Investigators are not obligated to actively seek AEs or SAEs after conclusion of the study participation. However, if the investigator learns of any SAE, including a death, at any time after a participant has been discharged from the study, and he/she considers the event to be reasonably related to the study intervention or study participation, the investigator must promptly notify the sponsor.

#### **8.3.1.1. Reporting SAEs to Pfizer Safety**

All SAEs occurring in a participant during the active collection period are reported to Pfizer Safety on the CT SAE Report Form immediately and under no circumstance should this exceed 24 hours, as indicated in [Appendix 3](#). The investigator will submit any updated SAE data to the sponsor within 24 hours of it being available.

SAEs occurring in a participant after the active collection period has ended are reported to Pfizer Safety if the investigator becomes aware of them; at a minimum, all SAEs that the investigator believes have at least a reasonable possibility of being related to IP must be reported to Pfizer Safety.

#### **8.3.1.2. Recording Nonserious AEs and SAEs on the CRF**

During the active collection period, both nonserious AEs and SAEs are recorded on the AE section of the CRF.

### **8.3.2. Method of Detecting AEs and SAEs**

The method of recording, evaluating, and assessing causality of AEs and SAEs and the procedures for completing and transmitting SAE reports are provided in [Appendix 3](#).

Care will be taken not to introduce bias when detecting AEs and/or SAEs. Open-ended and nonleading verbal questioning of the participant is the preferred method to inquire about AE occurrences.

### **8.3.3. Follow-up of AEs and SAEs**

After the initial AE/SAE report, the investigator is required to proactively follow each participant at subsequent visits/contacts. For each event, the investigator must pursue and obtain adequate information until resolution, stabilization, the event is otherwise explained, or the participant is lost to follow-up (as defined in [Section 7.3](#)).

In general, follow-up information will include a description of the event in sufficient detail to allow for a complete medical assessment of the case and independent determination of possible causality. Any information relevant to the event, such as concomitant medications and illnesses, must be provided. In the case of a participant death, a summary of available autopsy findings must be submitted as soon as possible to Pfizer Safety.

Further information on follow-up procedures is given in [Appendix 3](#).

### **8.3.4. Regulatory Reporting Requirements for SAEs**

Prompt notification by the investigator to the sponsor of an SAE is essential so that legal obligations and ethical responsibilities towards the safety of participants and the safety of a study intervention under clinical investigation are met.

The sponsor has a legal responsibility to notify both the local regulatory authority and other regulatory agencies about the safety of a study intervention under clinical investigation. The sponsor will comply with country-specific regulatory requirements relating to safety reporting to the regulatory authority, IRBs/ECs, and investigators.

Investigator safety reports must be prepared for suspected unexpected serious adverse reactions (SUSARs) according to local regulatory requirements and sponsor policy and forwarded to investigators as necessary.

An investigator who receives an investigator safety report describing an SAE or other specific safety information (eg, summary or listing of SAEs) from the sponsor will review and then file it along with the investigator's brochure and will notify the IRB/EC, if appropriate according to local requirements.

### **8.3.5. Exposure During Pregnancy or Breastfeeding, and Occupational Exposure**

Exposure to the investigational product under study during pregnancy or breastfeeding and occupational exposure are reportable to Pfizer Safety within 24 hours of investigator awareness.

#### **8.3.5.1. Exposure During Pregnancy**

Details of all pregnancies in female participants will be collected after the start of study intervention and until 28 calendar days after the last administration of IP.

If a pregnancy is reported, the investigator should inform the sponsor within 24 hours of learning of the pregnancy and should follow the procedures outlined in [Appendix 4](#).

Abnormal pregnancy outcomes (eg, spontaneous abortion, fetal death, stillbirth, congenital anomalies, ectopic pregnancy) are considered SAEs.

### 8.3.5.2. Exposure During Breastfeeding

Scenarios of exposure during breastfeeding must be reported, irrespective of the presence of an associated SAE, to Pfizer Safety within 24 hours of the investigator's awareness, using the CT SAE Report Form. An exposure during breastfeeding report is not created when a Pfizer drug specifically approved for use in breastfeeding women (eg, vitamins) is administered in accord with authorized use. However, if the infant experiences an SAE associated with such a drug's administration, the SAE is reported together with the exposure during breastfeeding.

### 8.3.5.3. Occupational Exposure

An occupational exposure occurs when, during the performance of job duties, a person (whether a healthcare professional or otherwise) gets in unplanned direct contact with the product, which may or may not lead to the occurrence of an AE.

An occupational exposure is reported to Pfizer Safety within 24 hours of the investigator's awareness, using the CT SAE Report Form, regardless of whether there is an associated SAE. Since the information does not pertain to a participant enrolled in the study, the information is not recorded on a CRF; however, a copy of the completed CT SAE Report Form is maintained in the investigator site file.

### 8.3.6. Medication Errors

Medication errors may result from the administration or consumption of the IP by the wrong participant, or at the wrong time, or at the wrong dosage strength.

Exposures to the IP under study may occur in clinical trial settings, such as medication errors.

Safety Event	Recorded on the CRF	Reported on the CT SAE Report Form to Pfizer Safety Within 24 Hours of Awareness
Medication errors	All (regardless of whether associated with an AE)	Only if associated with an SAE

Medication errors include:

- Medication errors involving participant exposure to the IP;
- Potential medication errors or uses outside of what is foreseen in the protocol that do or do not involve the study participant.

Such medication errors occurring to a study participant are to be captured on the medication error page of the CRF, which is a specific version of the AE page.

In the event of a medication dosing error, the sponsor should be notified within 24 hours.

Whether or not the medication error is accompanied by an AE, as determined by the investigator, the medication error is recorded on the medication error page of the CRF and, if applicable, any associated AE(s), serious and nonserious, are recorded on an AE page of the CRF.

Medication errors should be reported to Pfizer Safety within 24 hours on a CT SAE Report Form **only when associated with an SAE**.

#### **8.4. Treatment of Overdose**

For this study, any dose of IP greater than 16 blinded tablets of PF-06882961 within an approximate 24-hour time period  $\pm 2$  hours will be considered an overdose.

There is no specific antidote for overdose with PF-06882961. Treatment of overdose should consist of general supportive measures.

In the event of an overdose, the investigator/treating physician should:

1. Contact the medical monitor within 24 hours.
2. Closely monitor the participant for any AEs/SAEs and laboratory abnormalities for at least 5 half-lives or 28 calendar days after the overdose of PF-06882961 (whichever is longer).
3. Obtain a blood sample for PK analysis within 2 days from the date of the last dose of study intervention if requested by the medical monitor (determined on a case-by-case basis).
4. Document the quantity of the excess dose as well as the duration of the overdose in the CRF.
5. Overdose is reportable to Safety **only when associated with an SAE**.

Decisions regarding dose interruptions or modifications will be made by the investigator in consultation with the medical monitor based on the clinical evaluation of the participant.

CCI [REDACTED]

CCI [REDACTED]

[REDACTED]

[REDACTED]

[REDACTED]

[REDACTED]

[REDACTED]

### 8.6. Pharmacodynamics

PD parameters evaluated in this study include CCI [REDACTED] fasting plasma glucose CCI [REDACTED] and will be collected according to the SoA. The PD parameters will be assessed by the Central Laboratory as part of the clinical laboratory assessments (see [Appendix 2](#)).

CCI [REDACTED]  
[REDACTED]  
[REDACTED]  
[REDACTED]  
[REDACTED]  
[REDACTED]  
[REDACTED]

CCI [Redacted]

[Redacted]

[Redacted]

[Redacted]

[Redacted]

[Redacted]

[Redacted]

[Redacted]

[Redacted]

[Redacted]

[Redacted]

[Redacted]

CCI [Redacted]

[Redacted]

[Redacted]

## 8.9. Health Economics

Health economics/medical resource utilization and health economics parameters are not evaluated in this study.

## 9. STATISTICAL CONSIDERATIONS

Detailed methodology for summary and statistical analyses of the data collected in this study is outlined here and further detailed in a SAP, which will be maintained by the sponsor. The SAP may modify what is outlined in the protocol where appropriate; however, any major modifications of the primary endpoint definitions or their analyses will also be reflected in a protocol amendment.

### 9.1. Estimands and Statistical Hypotheses

#### 9.1.1. Estimands

A summary of estimands is provided in the table below and described in detail thereafter:

Variable	Estimand	Population	Intercurrent Event	Population-level Summary	International Council for Harmonisation (ICH)-E9(R1) Strategy(ies)
HbA1c (continuous)	1A	Metformin + Diet & Exercise	Absence of glycemic rescue medication and discontinuation of study IP	Mean difference (PF-06882961 versus Placebo)	Hypothetical While on treatment
CCI					
HbA1c (categorical)	2	Metformin + Diet & Exercise	Absence of glycemic rescue medication and discontinued from IP	Odds ratio (PF-06882961 relative to Placebo)	Hypothetical While on treatment
Fasting Plasma Glucose (continuous)	3	Metformin + Diet & Exercise	Absence of glycemic rescue medication and discontinuation of IP	Mean difference (PF-06882961 versus Placebo)	Hypothetical While on treatment
Body Weight (continuous)	4	Metformin + Diet & Exercise	Absence of glycemic rescue medication and discontinuation of IP	Mean difference (PF-06882961 versus Placebo)	Hypothetical While on treatment

*Estimands related to the change from baseline in HbA1c:*

The primary estimand (Estimand 1A) will be the population average treatment effect on the change from baseline in HbA1c at Week 16 of PF-06882961 compared to placebo in the absence of glycemic rescue medication while on treatment and stable doses of background metformin and/or diet and exercise. This reflects a combination of the ‘Hypothetical’ and ‘While on treatment’ strategies as outlined in the ICH-E9 (R1) draft guidance.

Measurements after initiation of glycemic rescue medication or discontinuation of IP will be censored and treated as missing data. Missing data due to censoring, study withdrawal or other reasons (eg, laboratory failure) will have data imputed based on a missing at random (MAR) assumption. Participants with inadequate compliance will have their HbA1c values used as-is in the analysis. The population-based treatment effect will be the difference in the mean change from baseline in each PF-06882961 arm compared to placebo. This estimand will similarly be applied to the changes from baseline in HbA1c at Weeks 2, 4, 6, 8, and 12.

CCI [REDACTED]

Any missing data (for example due to study withdrawal or laboratory failure) will have data imputed based on a MAR assumption. The population-based treatment effect will be determined for each individual time point based on the differences in the mean change from baseline in each PF-06882961 arm compared to placebo.

CCI [REDACTED]

*Estimands related to achieving HbA1c <7% at Week 16:*

A secondary estimand (Estimand 2) will be the population odds ratio of the treatment effect of achieving HbA1c <7% at Week 16 of PF-06882961 compared to placebo in the absence of glycemic rescue medication in participants while on treatment and on stable doses of background metformin and/or diet and exercise. This reflects a combination of the ‘Hypothetical’ and ‘While on treatment’ strategies as outlined in the ICH-E9 (R1) draft guidance.

Measurements after initiation of glycemic rescue medication and/or discontinuation of IP will be censored and treated as missing data. Missing data due to censoring, study withdrawal, or other reasons (eg, laboratory failure) may be imputed as outlined in the SAP. The population-based treatment effect will be the odds of achieving a HbA1c <7% at Week 16 on PF-06882961 compared to the odds of achieving this on placebo (ie, odds ratio).

*Estimands related to other endpoints:*

Estimands 3 and 4 will utilize the same approach as Estimand 1A for the associated endpoint(s).

CCI [REDACTED] Other estimands may be used for some of the primary and secondary endpoints as a means to examine the robustness of results, compare to available literature and/or be used for future study planning as needed. Details of these estimands and analyses will be presented in the SAP.

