### 9.4.1. Efficacy Analyses

Endpoint	Statistical Analysis Methods

Primary: Change from baseline in HbA1c at Week 16.
	
A MMRM analysis of the change from baseline in HbA1c through Week 16 will be used to estimate the treatment effect related to the primary Estimand 1A.
 
The MMRM will include treatment, time, strata (metformin vs. diet and exercise alone) and treatment-by-time interaction as fixed effects, baseline as a covariate and the baseline-by-time interaction with time fitted as a repeated effect and participant as a random effect. An unstructured correlation matrix will be used, and the Kenward-Roger approximation will be used for estimating degrees of freedom for the model parameters.
 
The MMRM model will be fitted to change from baseline to Weeks 2, 4, 6, 8, 12 and 16 from the Estimand Set 1A.
 
Missing values will be imputed as part of the MMRM model assumptions.
 
No adjustments will be made for multiplicity.

Secondary: Response as defined by an HbA1c <7% at Week 16.
	
A logistic regression analysis of participants who reached a HbA1c goal of <7% at Week 16 and those that didn't will be used to estimate the treatment effect related to the secondary estimand 2.
 
The logistic regression model will include a term for treatment, strata (metformin vs. diet and exercise alone), and baseline HbA1c will be included as a covariate.
 
This model will be fitted to the Week 16 timepoint only from the Estimand Set 1A. No adjustments will be made for multiplicity.

Secondary: Change from baseline in fasting plasma glucose through and at Weeks 2, 4, 6, 8, 12 and 16.
	
Changes from baseline in fasting plasma glucose at Weeks 2, 4, 6, 8, 12 and 16 will be analyzed using a similar MMRM model to that used for the primary endpoint. Baseline fasting plasma glucose will be included as a covariate in the model, rather than baseline HbA1c.
 
No adjustments will be made for multiplicity.
 
This analysis will be applied to the Estimand Set 1A to estimate the treatment effect related to Estimand 3.

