### 2.1.2. Secondary Estimand(s)

#### 2.1.2.1. Estimand Related to Achieving HbA1c <7% at Week 16

A secondary estimand (Estimand 2) will be the population odds ratio of the treatment effect of achieving HbA1c <7% at Week 16 of PF-06882961 compared to placebo in the absence of glycemic rescue medication in participants while on treatment and on stable doses of background metformin and/or diet and exercise. This reflects a combination of the 'Hypothetical' and 'While on treatment' strategies as outlined in the ICH-E9 (R1) draft guidance (1). It includes the following 4 attributes:

- Population: Defined by the inclusion and exclusion criteria to reflect participants with T2DM who are on a background of metformin and/or diet & exercise
- Variable: Response as defined by an HbA1c <7% at Week 16
- Intercurrent events: Any participant with an intercurrent event of glycemic rescue medication and/or discontinuation of IP prior to Week 16 will have all subsequent data

censored if not missing. Missing or censored values at Week 16 will be imputed (assuming missing at random [MAR]) to determine a response classification.

- Population-level summary: Odds ratio for a response between PF-06882961 (each dose considered separately) and placebo

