#### 5.2.4. Logistic Regression

*The logistic regression model will include a term for treatment, strata (metformin vs. diet and exercise alone), and baseline will be included as a covariate. The model will be fitted to the Week 16 timepoint only.*

Missing values (e.g. due to censoring) will be imputed for missing data using a multiple imputation method as described in Section 5.3.

The odds ratio for each dose of PF-06882961 relative to placebo and corresponding 90% confidence interval will be obtained.

Example SAS code is provided in Appendix 4.

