#### 6.2.1.1. Main Analysis

In all cases the Estimand Set 2 as specified in Section 4 will be utilised.

The proportion of responses at Week 16 will be summarised descriptively by treatment as described in Section 5.2.2, where no imputation for missing values will be conducted. The proportion of responses at Week 16 will also be reported after multiple imputation for missing values as per Section 5.3.

A logistic regression model (as described in Section 5.2.4) will be applied to the response at Week 16 that will be used to estimate the treatment effect related to the secondary Estimand 2 (as described in Section 2.1.2.1), where missing values will be imputed using multiple imputation as per Section 5.3. Baseline HbA1c and strata will be included in the model.

In addition, standard SAS output will be provided to support the main statistical summary table for the logistic regression model and multiple imputation approach but will not be included in the CSR.

#### 6.2.2. Change from Baseline in HbA1c at Weeks 2, 4, 6, 8 and 12

Summaries and analysis results will be reported as per the primary analysis approach (Section 6.1.1).

#### 6.2.3. Change from Baseline in Fasting Plasma Glucose at Weeks 2, 4, 6, 8, 12 and 16

In all cases the Estimand Set 1A as specified in Section 4 will be utilised.

Absolute values and changes from baseline in fasting plasma glucose will be summarised similar to HbA1c in Section 6.1.1.1.

The analysis will be an MMRM (as described in Section 5.2.3) applied to the change from baseline at Weeks 2, 4, 6, 8, 12 and 16 that will be used to estimate the treatment effect related to the primary Estimand 3 (as described in Section 2.1.1). Results similar to HbA1c in Section 6.1.1.1 (excluding the waterfall plot) will be reported along with standard SAS output (where the latter will not be included in the CSR).

#### 6.2.4. Change from Baseline in Body Weight at Weeks 2, 4, 6, 8, 12 and 16

In all cases the Estimand Set 1A as specified in Section 4 will be utilised.

Absolute values and changes from baseline in body weight will be summarised similar to HbA1c in Section 6.1.1.1.

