    model resp = treatment strata base/alpha=0.1;
    oddsratio dose/diff=all;
    ods output OddsRatiosWald=OddsRatiosWald_mi;
run;

data OddsRatiosWald_mi;
    set OddsRatiosWald_mi;
    if Effect = 'treatment 2.5 mg BID vs Placebo' then treatment = 2.5;
    if Effect = 'treatment 10 mg BID vs Placebo' then treatment = 10;
    if Effect = 'treatment 40 mg BID vs Placebo' then treatment = 40;
    if Effect = 'treatment 80 mg BID vs Placebo' then treatment = 80;
    if Effect = 'treatment 120 mg BID vs Placebo' then treatment = 120;
    if treatment = . then delete;
    estimate = log(OddsRatioEst);
    SE = (log(UpperCL) - log(LowerCL))/(2*QUANTILE('NORMAL',0.95));
run;

proc sort data=OddsRatiosWald_mi;
    by treatment _imputation_;
proc mianalyze data=OddsRatiosWald_mi alpha=0.1;
    by treatment;
    modeleffects estimate;
    stderr SE;
    ods output parameterestimates=OddsRatiosWald_mi_out;
run;
```

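### Estimand 2 is stated as a population odds ratio, but the planned baseline-adjusted logistic model reports a conditional one, which lies further from 1 whenever there is an effect

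*Protocol*

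**What the plan says.** **The target.**

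- Protocol 9.1.1: "The population-based treatment effect will be the odds of achieving a HbA1c <7% at Week 16". This is for participants given the drug, and it is set against the same odds under placebo. The definition conditions on neither baseline HbA1c nor stratum.
- SAP 2.1.2.1: "A secondary estimand (Estimand 2) will be the population odds ratio of the treatment effect of achieving HbA1c <7% at Week 16". Its attribute list is shorter: "Population-level summary: Odds ratio for a response between PF-06882961 (each dose considered separately) and placebo".

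**The estimator.**

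- Protocol 9.4.1 plans a logistic regression on treatment and stratum, "and baseline HbA1c will be included as a covariate".
- SAP 6.2.1.1 applies this regression to the Week 16 response and says of it: "that will be used to estimate the treatment effect related to the secondary Estimand 2".
- SAP 5.2.4 states the output: "The odds ratio for each dose of PF-06882961 relative to placebo and corresponding 90% confidence interval will be obtained".
- SAP 5.3.1 pools the model's log odds ratios over 20 imputed datasets by Rubin's rules and back-transforms them.
- The Appendix 4 code has the line "model resp = treatment strata base/alpha=0.1" and no standardisation step after it.

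SAP 5.3.1 and 6.2.1.1 also report response proportions by arm after multiple imputation. No odds ratio is planned from them.

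**The concern.** For a mean difference, as in Estimand 1A, adjusting for a baseline covariate under randomisation sharpens the estimate without changing what is estimated. An odds ratio does not behave this way. If a covariate predicts response and the effect is not null, the odds ratio within levels of the covariate is further from 1 than the odds ratio formed from the two population response rates. This holds with perfect randomisation and no missing data.

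Baseline HbA1c must predict this endpoint, because Week 16 HbA1c is baseline plus change, cut at 7% (Appendix 4 rebuilds it that way). The number reported for Estimand 2 therefore answers a different question from the one in Protocol 9.1.1. The gap grows with the effect, so it is largest for the most effective doses, in a study meant to inform dose selection. A reader who forms an odds ratio from the tabulated proportions will get a different and smaller figure.

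**Working it through.** **1. The plan's own figure.** The only design figure is for the primary endpoint (Protocol 9.2): 50 completers per arm, difference 0.5%, SD 1.0%, one-sided 5%.

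- SE = 1.0 × √(2/50) = 0.20, and 0.5/0.20 = 2.5.
- Power = Φ(2.5 − 1.645) = 80.4% (79.9% by the noncentral t). The stated 80% is reproduced.
- 50/0.75 = 66.7, so 67 per arm.

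No responder rate, odds ratio or baseline SD is given for Estimand 2.

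**2. Set-up for the comparison.** Week 16 HbA1c = baseline + change, with response if <7%. Assumptions:

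- baseline normal with mean 8.2, truncated to the 7-10.5% screening range (Protocol 5.1), SD after truncation 0.63-0.82
- mean placebo change 0
- slope of change on baseline −0.3 or −0.5
- residual SD 0.75-0.95, giving an SD of change of 0.77-0.99, close to the protocol's 1.0

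Stratum was not simulated. Three quantities were compared in very large samples:

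- marginal OR = [p1/(1−p1)] / [p0/(1−p0)], from the arm response rates
- model OR = exp(treatment coefficient), from logistic regression on treatment and baseline
- standardised OR, from the same fitted model with predicted probabilities averaged over everyone under drug and under placebo

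**3. One case by hand** (baseline SD 0.75, slope −0.3, residual SD 0.95, effect 1.0%). Response is 10.7% on placebo and 37.7% on drug.

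- Odds are 0.107/0.893 = 0.120 and 0.377/0.623 = 0.605.
- Their ratio is about 5.05 (5.07 before rounding the rates).
- The model OR is 6.20, and 6.20/5.07 = 1.22.
- The standardised OR is 5.07.

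**4. Range with truncated baseline.** The table shows the lowest, a middle and the highest ratio for each effect.

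| Effect | Baseline SD, slope, residual SD | Response, placebo v drug | Marginal OR | Model OR | Ratio |
|---|---|---|---|---|---|
| 0.5% | 0.63, −0.5, 0.90 | 9.2% v 21.1% | 2.63 | 2.74 | 1.04 |
| 0.5% | 0.75, −0.3, 0.95 | 10.6% v 21.8% | 2.34 | 2.56 | 1.09 |
| 0.5% | 0.82, −0.3, 0.75 | 6.3% v 16.5% | 2.92 | 3.42 | 1.17 |
| 1.0% | 0.63, −0.5, 0.90 | 9.2% v 39.3% | 6.36 | 7.04 | 1.11 |
| 1.0% | 0.75, −0.3, 0.95 | 10.7% v 37.7% | 5.07 | 6.20 | 1.22 |
| 1.0% | 0.82, −0.3, 0.75 | 6.3% v 33.1% | 7.33 | 10.63 | 1.45 |

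With no effect the ratio is 1.00 throughout. In every setting the standardised OR equals the marginal OR to within simulation error.

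**5. Without truncation.** The 7-10.5% limits apply at screening, while baseline is the last value before Day 1 dosing, so the Day 1 spread may be wider. With mean 8.1, SD 0.9 and SD of change about 0.8-1.0, the model OR exceeds the marginal OR by:

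- 11-33% (0.5% effect) and 24-78% (1.0% effect) with slopes −0.3 to −0.5
- 28-49% and 65-123% with no regression to the mean

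**6. At trial size.** In 1,498 simulated comparisons of 67 per arm (the step 3 case, no missing data), the median odds ratios were 5.23 unadjusted, 6.56 from the model and 5.22 standardised. The model value was further from 1 than the standardised value in every one. The SD of the log odds ratio was 0.51 unadjusted and 0.48 standardised, so standardising did not lose the precision gained from the covariate.

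**The case against.** The strongest reply is that neither document uses the words marginal or conditional, and that both name the adjusted model as the estimator for this estimand, so the wording may simply be loose around an intended adjusted odds ratio. Part of this stands. The SAP's population-level summary only implies a marginal effect. But Protocol 9.1.1 spells out odds on drug against odds on placebo for the population, and the SAP keeps the term population odds ratio. Naming a model in advance does not make it estimate that quantity.

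Second, the adjusted odds ratio is a legitimate effect measure. A reader might infer that the plan's estimate is biased or its test invalid. The documents do not support that: both odds ratios equal 1 under the null, so the test in SAP 5.1 stands, and the model estimates its own conditional effect properly. Nor are the primary endpoint, its power or the Emax analyses touched, since they use continuous HbA1c.

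Third, the imprecision is large. With 67 per arm and a 0.5% effect, the upper 90% limit is about 4.9 times the lower, so a shift at the low end of the range is small beside it. That is fair for modest effects and less so at high doses.

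Fourth, the multiply-imputed proportions already let a reader work out a population odds ratio. True, but no such odds ratio with a confidence interval is planned.

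**Conclusion.** The mismatch is real. The stated target is a population odds ratio, the planned number is conditional on baseline HbA1c and stratum, and the latter lies further from 1 whenever there is an effect. It concerns the size and label of a secondary estimate, and the plan should be changed to resolve it.

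The direction does not depend on the assumptions, but the size does. With Day 1 HbA1c mean about 8.1-8.2, SD about 0.6-0.9, residual SD 0.75-1.0 and slope of change on baseline 0 to −0.5, the conditional odds ratio is roughly 5-50% larger for a 0.5% effect and 10-120% larger for a 1.0% effect. With baseline truncated to 7-10.5% and some regression to the mean, the figures are about 4-17% and 10-45%.

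These are rough ranges over plausible settings, not bounds. A wide baseline spread with a small residual SD and no regression to the mean goes higher, and the opposite combination goes a little lower. A reader might want a single inflation figure; without a baseline SD or responder rate in the documents, none can be defended.

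**What to change.** In SAP 5.2.4, 5.3.1 and Appendix 4, keep the same logistic model in each imputed dataset and add these steps:

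1. Average the predicted response probabilities over all evaluable participants, with treatment set in turn to each dose and to placebo.
2. Form the marginal log odds ratio for each dose against placebo, with a delta-method SE.
3. Pool over imputations by Rubin's rules and back-transform.
4. Report this with its 90% confidence interval as the Estimand 2 estimate. Keep the model odds ratio as supportive, labelled as conditional on baseline HbA1c and stratum.

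If the sponsor intends the conditional effect, the minimum is to redefine Estimand 2 in Protocol 9.1.1 and SAP 2.1.2.1 as conditional on baseline HbA1c and stratum, and to label the reported odds ratio that way.

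The cost of the main fix is a short SAP text change and a little more code, with no new data. The headline odds ratio will look less favourable.
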